5.1.2 Concomitant medication date imputation

5.1.2.1 Concomitant medication end date imputation

Rules for imputing the CM end date are stated below. Date of last contact in the study has been defined as in Section 2.1.3.10. Concomitant medication end dates will not be imputed for ongoing records.

1. If CM end day is missing and CM month/year are non-missing then impute CM day as the minimum of date of last contact and the last day of the month.
2. If CM end day/month are missing and CM year is non-missing then impute CM day as the minimum of date of last contact and the end of the year (31DECYYYY).
3. If CM day/month/year is missing then use the date of last contact + 1 day as the imputed CM end date.
4. If imputed CM end date is less than the CM start date, use the CM start date as the imputed CM end date.

5.1.2.2 Concomitant medication start date imputation

Rules for imputing the CM start date:

The following table explains the notation used in the logic matrix. Please note that **missing start dates** will not be imputed.

	Day	Month	Year
Partial CMD Start Date	Not Used	MON	YYYY
Treatment Start Date	Not Used	TRTM	TRTY

The following matrix explains the logic behind the imputation.

	MON MISSING	MON < TRTM	MON = TRTM	MON > TRTM
YYYY MISSING	(1) Uncertain	(1) Uncertain	(1) Uncertain	(1) Uncertain
YYYY < TRTY	(2.a) Before Treatment Start	(2.b) Before Treatment Start	(2.b) Before Treatment Start	(2.b) Before Treatment Start
YYYY = TRTY	(4.a) Uncertain	(4.b) Before Treatment Start	(4.a) Uncertain	(4.c) After Treatment Start
YYYY > TRTY	(3.a) After Treatment Start	(3.b) After Treatment Start	(3.b) After Treatment Start	(3.b) After Treatment Start

1. If the CM start date year value is missing, the imputed CM start date is set to one day prior to treatment start date.
2. If the CM start date year value is less than the treatment start date year value, the CM started before treatment. Therefore:
 - a. If the CM month is missing, the imputed CM start date is set to the mid-year point (01JulYYYY).

- b. Else if the CM month is not missing, the imputed CM start date is set to the midmonth point (15MONYYYY).
3. If the CM start date year value is greater than the treatment start date year value, the CM started after treatment. Therefore:
 - a. If the CM month is missing, the imputed CM start date is set to the year start point (01JanYYYY).
 - b. Else if the CM month is not missing, the imputed CM start date is set to the month start point (01MONYYYY).
4. If the CM start date year value is equal to the treatment start date year value:
 - a. And the CM month is missing or the CM month is equal to the treatment start date month, then the imputed CM start date is set to one day prior treatment start date.
 - b. Else if the CM month is less than the treatment start date month, the imputed CM start date is set to the mid-month point (15MONYYYY).
 - c. Else if the CM month is greater than the treatment start date month, the imputed CM start date is set to the month start point (01MONYYYY).

If complete imputed CM end date is available and the imputed CM start date is greater than the (imputed) CM end date, then imputed CM start date should be set to the (imputed) CM end date.

5.2 AEs coding/grading

The MedDRA version which will be available at the time of database lock, will be used for the coding purpose of the adverse events. For coding purpose of the concomitant medications, the available WHO-DD (World Health Organization-Drug Dictionary) version at the time of database lock, will be used.

5.3 Laboratory parameters derivations

The following table shows the criteria for clinically notable laboratory values. Not all parameters have notable criteria defined.

Table 5.3.1 Direction of interest for worst case value for laboratory parameters

Laboratory Parameter	Direction of interest for worst case value
A. Hematology	
Basophils	High
Eosinophils	High
Hematocrit	Low
Hemoglobin	Low
Lymphocytes	Low and high
Monocytes	High
Neutrophils	Low and high
Platelets	Low and high
RBC	Low
WBC total	Low and high
B. Chemistry	
Albumin	Low
Sodium	Low and High
Alkaline Phosphatase	High
ALT/SGPT	High
AST/SGOT	High
Bilirubin Total	High
Blood Urea Nitrogen (BUN)	High
CPK	High
Creatinine	High
Gamma GT	High
Glucose	Low and high
Potassium	Low and high
Uric acid	High

Table 5.3.2 Clinical notable criteria for selected laboratory tests

Laboratory parameter (unit)	Bound for notably low values	Bound for notably high values
Hematology		
Hematocrit (v/v)		
Male 12-17	0.34	
Male 18-65	0.37	
Male >=66	0.34	
Female 12-65	0.32	
Female >=66	0.31	

Laboratory parameter (unit)	Bound for notably low values	Bound for notably high values
Hemoglobin (g/L)		
Male 12-17	100	
Male >=18	110	
Female	95	
Thrombocytes (x10E ⁹ /L)	75	700
WBC's (x10 ⁹ /L)	2.8	16.0
Chemistry		
Alkaline Phosphatase (IU/L)	-	3xULN
Total Bilirubin (µmol/L)	-	34.2
Creatinine (µmol/L)		176.8
Potassium (mmol/L)	3	6
Glucose (mmol/L)	2.78	9.99
ALT/SGPT (U/L)	-	3 x ULN
AST/SGOT (U/L)	-	3 x ULN
BUN/ Urea (mmol/L)		9.99
Sodium (mmol/L)	125	160
Gamma GT (U/L)		3 x ULN
CPK (IU/L)		4 x ULN

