#### 8.4.1 Laboratory evaluations

Samples for safety will be collected as per the assessment schedule in [Table 8-1](#). A central laboratory will be used for analysis of all specimens detailed in this section. Details on the collections, shipment of samples and reporting of results by the central laboratory are provided to Investigators in the laboratory manual.

Details on clinically notable laboratory findings are defined in [Section 16.1](#).

[figure not shown]

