### 16.1 Appendix 1: Clinically notable laboratory values and vital signs

The central laboratory will flag laboratory values falling outside of the normal ranges on the central laboratory reports. Investigators are responsible for reviewing these abnormal values for clinical significance, signing the laboratory reports to indicate their review, and reporting values considered clinically significant in the appropriate electronic case report form (eCRF).

Any clinically significant abnormal laboratory value should be evaluated and followed-up by the Investigator until normal or a cause for the abnormality is determined.

See [Section 16.2](#) for specific liver event and laboratory test trigger definitions and follow-up requirements. See [Section 16.3](#) for specific renal alert criteria and actions.

For electrocardiograms (ECGs), a notable QTc value is defined as a QTcF (Fridericia) interval of  $\geq 450$  msec for males or  $\geq 460$  msec for females. All ECGs will be assessed locally at site and with assessment of clinical relevance and continuance of the patient being confirmed by the Investigator.

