> 3 to ≤ 5 × ULN (patient is asymptomatic)	
 
Repeat LFT within the next week
 
If elevation is confirmed, initiate close observation of the patient
 
	Investigator discretion Monitor LFT within 1 to 4 weeks
ALP (isolated)		
> 2 × ULN (in the absence of known bone pathology)	
 
Repeat LFT within 48 hours
 
If elevation persists, establish causality
 
Record the AE and contributing factors (e.g., conmeds, med hx, lab) in the appropriate CRF
 
	Investigator discretion Monitor LFT within 1 to 4 weeks or at next visit
TBL (isolated)		
> 2 × ULN (in the absence of known Gilbert syndrome)	
 
Repeat LFT within 48 hours
 
If elevation persists, discontinue the study drug immediately
 
Hospitalize if clinically appropriate
 
Establish causality
 
Record the AE and contributing factors (e.g., conmeds, med hx, lab) in the appropriate CRF
 
	ALT, AST, TBL, Alb, PT/INR, ALP and γGT until resolution c (frequency at Investigator discretion) Test for hemolysis (e.g., reticulocytes, haptoglobin, unconjugated [indirect] bilirubin)
> 1.5 to ≤ 2 × ULN (patient is asymptomatic)	
 
Repeat LFT within the next week
 
If elevation is confirmed, initiate close observation of the patient
 
	Investigator discretion Monitor LFT within 1 to 4 weeks or at next visit
Jaundice	
 
Discontinue the study treatment immediately
 
Hospitalize the patient
 
Establish causality
 
Record the AE and contributing factors (e.g., conmeds, med hx, lab) in the appropriate CRF
 
	ALT, AST, TBL, Alb, PT/INR, ALP and γGT until resolution c (frequency at Investigator discretion)
Any AE potentially indicative of a liver toxicity	
 
Consider study treatment interruption or discontinuation
 
Hospitalization if clinically appropriate
 
Establish causality
 
Record the AE and contributing factors (e.g., conmeds, med hx, lab) in the appropriate CRF
 
	Investigator discretion

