### 16.3 Appendix 3: Specific Renal Alert Criteria and Actions and Event Follow-up

**Table 16-3 Specific Renal Alert Criteria and Actions**

Serum Event	
Serum creatinine increase 25 – 49% compared to baseline	Confirm 25% increase after 24-48h Follow up within 2-5 days
Acute Kidney Injury: Serum creatinine increase ≥50% compared to baseline	Follow up within 24-48h if possible Consider study treatment interruption Consider patient hospitalization /specialized treatment
Urine Event	
Albumin-creatinine ratio (ACR) ≥1g/g or ≥100 mg/mmol; Protein-creatinine ratio (PCR ) ≥1g/g or ≥100 mg/mmol	Confirm value after 24-48h Perform urine microscopy Consider study treatment interruption / or discontinuation
For all renal events:	

Document contributing factors in the CRE: co-medication, other co-morbid conditions, and additional diagnostic procedures performed
 
Monitor patient regularly (frequency at investigator's discretion) until either:
 
Event resolution: sCr within 10% of baseline or protein-creatinine ratio within 50% of baseline, or
 
Event stabilization: sCr level with ±10% variability over last 6 months or protein-creatinine ratio stabilization at a new level with ±50% variability over last 6 months.
	

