2.8.2 Vital signs

Vital signs measurements include systolic and diastolic blood pressure (SBP and DBP), pulse rate, temperature, height and body weight. Vital signs data taken on or after the time of the first intake of study treatment and until the day after the last intake of study drug are regarded as on-treatment data. Vital signs data measured more than 1 day after last intake of study drug are

regarded as post-treatment data and will not be summarized. All data will be included in the analyses regardless of rescue medication use.

The following analyses will be performed by treatment group:

- the number and percentage of patients with newly occurring or worsening notable vital signs on-treatment values (see [Table 2.8.2](#) for definition of notable values) summarized by parameter (except height), at any time on treatment considering all post-baseline data from scheduled, unscheduled and premature discontinuation visits
- Vital signs will also be summarized by clinically relevant categories at the baseline and the week 16 visits :
 1. Pulse rate: < 40 bpm, 40 – 90 bpm, and > 90 bpm
 2. Systolic blood pressure: < 90 mm Hg, 90 – 140 mm Hg, and > 140 mm Hg
 3. Diastolic blood pressure: < 50 mm Hg, 50 – 90 mm Hg, and > 90 mm Hg.

The same approach as for notable laboratory values will be used to define a newly occurring notable vital sign value and a worsening notable vital sign value.

A listing of all patients with notable vital sign values and changes will be provided.

Table 2.8.2 Clinical notable criteria for vital signs

Vital sign parameter (unit)	Lower bound of clinically notable range	Upper bound of clinically notable range
Notable values		
Systolic blood pressure (mmHg)	< 75	> 200
Diastolic blood pressure (mmHg)	< 40	> 115
Pulse rate (bpm)	< 40	> 130
Notable change from baseline		
Systolic blood pressure (mmHg)	≤ 90 and decrease from baseline by ≥ 20	≥ 180 and increase from baseline by ≥ 20
Diastolic blood pressure (mmHg)	≤ 50 and decrease from baseline by ≥ 15	≥ 105 and increase from baseline by ≥ 15
Pulse rate (bpm)	≤ 50 and decrease from baseline by ≥ 15	≥ 120 and increase from baseline by ≥ 15
Weight (kg)	Decrease ≥ 7% from baseline	Increase ≥ 7% from baseline

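### The SAP's notable-value table uses creatinine and ALP bounds that leave uncounted some patients who meet the protocol's own renal and liver criteria

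*SAP*

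**What the plan says.** Protocol 8.4.1 states: "Details on clinically notable laboratory findings are defined in" Section 16.1. Section 16.1 gives no numeric laboratory bounds of its own. It refers to 16.2 for liver criteria and to 16.3 "for specific renal alert criteria and actions".

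- **Renal.** Table 16-3 has two serum tiers, both relative to the patient's own baseline: "Serum creatinine increase 25 – 49% compared to baseline" and "Acute Kidney Injury: Serum creatinine increase ≥50% compared to baseline". Protocol 10.2.2 adds that the 25% event must be confirmed after at least 24 hours, under normal hydration.
- **Liver.** Table 16-1 makes ALP above 2 × ULN a liver event; the matching row of Table 16-2 reads "> 2 × ULN (in the absence of known bone pathology"). Table 16-1 also defines a potential Hy's Law case jointly: ALT or AST above 3 × ULN with total bilirubin above 2 × ULN, and ALP not raised above 2 × ULN.

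The protocol's analysis section (12.5.1, clinical laboratory evaluations) promises counts of patients with newly occurring or worsening clinically notable values for selected parameters. SAP 2.7.7.2 takes its criteria for these counts from "Table 5.3.2 Clinical notable criteria for selected laboratory tests". The whole creatinine entry there is "Creatinine (µmol/L) 176.8". ALP is set at 3 × ULN, ALT and AST at 3 × ULN each, and total bilirubin at 34.2 µmol/L, all as single-parameter rows. SAP section 4 records no change to the protocol-specified analyses.

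A smaller mismatch sits in SAP Table 2.8.2, which counts weight change ("Decrease ≥ 7% from baseline", and the corresponding increase). Protocol Table 8-1 schedules body weight at Screening only.

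**The concern.** General safety is a stated secondary objective, and Amendment 2 added renal monitoring to the trial. The protocol judges renal change against the patient's own baseline, whereas the SAP table judges it against one fixed concentration. In a population screened for adequate renal function (exclusion criterion 34 removes eGFR below 55), a fixed high bound is reached only after a rise far larger than those the protocol acts on.

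At stake is the by-arm comparison. If several patients in one dose group had confirmed rises of 25% or 50%, the notable-creatinine row could read zero in all arms. One patient is about 3% of an arm (1/31 = 3.2%), so a difference of two or three patients is easily lost without an explicit count.

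**Working it through.** No figure in the plan is being reproduced here, since 176.8 µmol/L is a fixed bound and not a calculated result. The check is threshold arithmetic.

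**Inputs.** Creatinine bound 176.8 µmol/L, ALP bound 3 × ULN and bilirubin bound 34.2 µmol/L (SAP Table 5.3.2). Creatinine tiers 25–49% and at least 50% (protocol Table 16-3). ALP event above 2 × ULN and bilirubin event above 2 × ULN (protocol Table 16-1). The documents give no baseline creatinine distribution and no laboratory ULN, so the baselines and ULNs below are assumptions.

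**Creatinine.** The lowest baseline from which a rise r reaches the bound is 176.8/(1 + r).

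- r = 25%: 176.8/1.25 = 141.4 µmol/L
- r = 50%: 176.8/1.50 = 117.9 µmol/L
- r = 100%: 176.8/2 = 88.4 µmol/L

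The rise needed to be counted from a given baseline is 176.8/baseline − 1.

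| Assumed baseline (µmol/L) | After +25% | After +50% | Rise needed to be counted |
|---|---|---|---|
| 60 | 75 | 90 | 195% |
| 80 | 100 | 120 | 121% |
| 100 | 125 | 150 | 77% |
| 110 | 137.5 | 165 | 61% |

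None of the 25% or 50% rises in the table reaches 176.8. The SAP does not say whether its bounds are inclusive, but that does not affect these rows.

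**ALP.** The protocol event starts above 2 × ULN and the SAP count starts at 3 × ULN. Values above 2 and up to 3 × ULN are protocol liver events that the table leaves out.

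**ALT/AST.** The SAP bound of 3 × ULN is the lower limit of the protocol's trigger (above 3 and up to 5 × ULN) and lies below its event limit (above 5 × ULN). There is no gap here. Every potential Hy's Law case has ALT or AST above 3 × ULN, so each one arising on treatment from a non-notable baseline enters the ALT or AST row. Exclusion criterion 34 already removes ALT or AST above 2 × ULN at Screening. What the separate rows cannot show is how many patients also met the bilirubin condition.

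**Bilirubin.** 34.2 µmol/L equals 2 × ULN only if ULN = 34.2/2 = 17.1 µmol/L. Over an assumed ULN of 15 to 24 µmol/L it corresponds to 34.2/15 = 2.28 down to 34.2/24 = 1.43 × ULN. Agreement with the protocol therefore depends on a ULN that the documents do not state.

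**Other displays.** SAP 2.7.7.1 summarises the worst on-treatment change from baseline by arm with descriptive statistics. SAP 2.7.7.2 adds box plots of change over time for creatinine and for the transaminases and total bilirubin. SAP 2.7.7 lists all values. These show size and spread; none counts patients at or above 25% or 50%.

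**Data available.** Table 8-1 schedules clinical chemistry at Screening, Day 1, Week 8 and Week 16. Urinalysis is scheduled only at Screening and Day 1, there is no coagulation row, and there is no weight after Screening.

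**The case against.** The case for leaving the SAP alone has substance.

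- **Alert criteria are not tabulation criteria.** Tables 16-1 to 16-3 drive patient-level actions. Protocol 12.5.1 names no thresholds and does not cite 16.2 or 16.3, and separate bounds for summary tables are common practice. This softens the mismatch but does not remove it, because 8.4.1 says in terms that the notable definitions lie in 16.1, which leads only to those tables. Table 5.3.2 also carries rows for ages 12–17 in a trial of adults, which suggests that it was not tailored to this protocol.
- **Creatinine is displayed by arm.** This is true: the summary of worst change includes a maximum, so one extreme value would show. It would be an absolute change, however, and would not say how many patients crossed a relative limit.
- **Adverse event tables catch liver cases.** Table 16-2 requires an adverse event record for potential Hy's Law cases, for ALT/AST above 5 × ULN and for ALP or isolated bilirubin above 2 × ULN, with a repeat test first for some of these. Those records reach the by-arm tables in SAP 2.7.5. The route is less certain for renal events: Table 16-3 asks for contributing factors to be documented but does not itself require an adverse event record. Special-interest tables depend on a retrieval strategy that the documents do not show. A BUN/urea row might flag some renal patients indirectly.

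A reader might infer that an excess of potential Hy's Law cases would go unseen. The documents do not support that, since each case appears in the ALT or AST row and notable values are listed by patient and treatment group. A reader might also infer that the weight row can only be empty. That goes too far, because SAP 2.8.2 admits unscheduled visits; what is certain is that no post-baseline weight is scheduled. Temperature is named among the vital signs in SAP 2.8.2 but has no criterion or category there, so there is no temperature criterion to remove.

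**Conclusion.** The point holds in a limited form. The SAP's notable-value counts do not follow the criteria to which protocol 8.4.1 and 16.1 refer. For creatinine, a 25% rise is uncounted from any baseline below 141.4 µmol/L and a 50% rise from any baseline below 117.9 µmol/L. For ALP, protocol events above 2 and up to 3 × ULN are uncounted. For the combined liver criterion, only the joint count is missing.

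A reader might conclude that renal signals would vanish from the report. They would not: the values are summarised, plotted and listed. The defect is that no named table counts, by arm, the patients who meet the protocol's creatinine criteria.

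The thresholds follow from the documents' figures alone. How many patients are affected depends on baseline creatinine, which the documents do not give. The eGFR exclusion makes the high baselines at which the SAP bound would work less likely. The primary analysis is untouched. This is an inexpensive improvement to the secondary safety displays, and it implies no view on which clinical action limits are right.

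**What to change.** In SAP 2.7.7.2 and Table 5.3.2, add counts by treatment arm for:

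- creatinine rise from baseline of 25–49% and of at least 50%, with confirmed and unconfirmed rises shown separately, because the protocol's 25% event needs confirmation after at least 24 hours. Program the two bands so that no value falls between them, and footnote that hydration status cannot be derived from the laboratory values;
- ALP above 2 × ULN;
- ALT or AST above 3 × ULN with total bilirubin above 2 × ULN and ALP not above 2 × ULN, stating whether the values must come from the same sample.

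Keep the existing bounds as extra rows, and record in SAP section 4 how the two sets of criteria relate. Footnote that the ALP count does not apply the protocol's bone-pathology qualifier unless that is adjudicated.

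Report the ACR/PCR and INR criteria only as a listing of unscheduled follow-up results, since no post-baseline values are scheduled and a table of counts would mislead. In SAP Table 2.8.2, remove the weight-change row or footnote that no post-baseline weight is scheduled.

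The cost is a few table rows and one programmed confirmation rule. The chemistry is already collected at Day 1, Week 8 and Week 16, so no visit, sample or clinical rule changes.

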5.4 Statistical models

5.4.1 Primary analysis

The primary endpoint for this study is the efficacy in terms of change from baseline in the nasal polyp score of fevipiprant 450 mg plus SoC and fevipiprant 150 mg plus SoC over placebo plus SoC.

The following mixed model with repeated measures will be used for changes from baseline in the Nasal Polyp Score :

Change from baseline = intercept + treatment + visit + treatment * visit + NPS baseline value + NPS baseline value * visit + error

The random effect in the mixed model will be represented by the use of an unstructured covariance matrix for the within patient variability.

The SAS procedure MIXED will be used with the following code :

```
proc mixed data=...order=internal;
  **include schedule assessments/visits only;
  where avisitn in (201,208,216);
  class trt avisitn;
  model chg= trt avisitn trt*avisitn base base*avisitn /ddfm=kr;
  repeated avisitn/subject=usubjid type=un;
  lsmeans trt*avisitn/ cl diff;
```

```
adjust=DUNNET;
```

```
run;
```

where chg = change from baseline

trt = treatment (QAW 450 mg + SoC , QAW 150 mg +SoC , Placebo+SoC)

avisitn = visit (include scheduled visit and assesments only)

base = baseline Nasal Polyp Score

usbjid = unique subject identifier

Appropriate baseline values and visits will be included for each of the endpoints i.e. Nasal Congestion Score, SNOT-22 score and the UPSIT smell test score.

The default estimation method for the covariance parameters will be used, which is the restricted maximum likelihood.

Results will be presented with least square means and standard errors (SE) for treatment effects and least square mean, SE, associated two sided 95% confidence interval , a two sided p-value for treatment contrast QAW-Placebo at each visit.

If the analysis fails to converge with an unstructured covariance matrix, either a compound symmetry (first choice) or the first order auto regressive (AR1) (second choice) covariance structure will be used.

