**Table 8-2 Nasal Polyp Scale**

Polyp Score	Polyp Size
0	No polyps
1	Small polyps in the middle meatus not reaching below the inferior border of the middle turbinate
2	Polyps reaching below the lower border of the middle turbinate
3	Large polyps reaching the lower border of the inferior turbinate or polyps medial to the middle turbinate
4	Large polyps causing complete obstruction of the inferior nasal cavity

NPS will be re-assessed at Treatment Day 1 to both re-confirm eligibility for the study but also for a baseline measurement. The central reading result must be received for the baseline assessment, prior to randomization. At the 8 and 16-week treatment visits, NPS will again be re-assessed for efficacy. The readings from the endoscopies performed will be uploaded for central reading for NPS determination.

The nasal endoscopy may be performed on a different day from the other study procedures as long as this is performed within approximately 5 days of the original scheduled visit.

Note that the nasal endoscopy procedure should not be performed within 3 days of any concomitant use of oral or nasal decongestants.

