The primary efficacy variable will be analyzed using a mixed model repeated measures (MMRM) approach (fevipiprant 450 mg plus SoC and fevipiprant 150 mg plus SoC). The model will include change from baseline to follow-up timepoints every 8 weeks through week 16 as response variables, fixed-effects factors for treatment, visit, treatment \times visit interaction, nasal

polyp score baseline value, and baseline \times visit interaction. An unstructured correlation structure will be assumed for the repeated measures within patients. Parameters will be estimated using the restricted maximum likelihood method with the Newton- Raphson algorithm. The least square mean change in nasal polyp score from baseline to week 16 alongside with 95% confidence interval and the P-value corresponding to the least square mean difference will be presented. The change in the least square mean will also be plotted by visit.

The change from baseline in NPS will be summarized by treatment arm and timepoint

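### The primary MMRM code selects visit 201, apparently baseline, against the SAP's own model text; if zero changes are stored there, the stated fallback would understate the Week 16 standard error

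*SAP*

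**What the plan says.** **Model text.** SAP 2.5.2 takes as outcomes the changes from baseline at "follow-up timepoints every 8 weeks through week 16 as response variables". Only Weeks 8 and 16 qualify. Protocol 8.3.1 agrees: the only endoscopies after the start of treatment are at those two visits. Of the earlier one it says "NPS will be re-assessed at Treatment Day 1 to both re-confirm eligibility for the study but also for a baseline measurement".

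**Code.** SAP 5.4.1 selects visits with "where avisitn in (201,208,216", fits "model chg= trt avisitn trt*avisitn base base*avisitn /ddfm=kr" and sets the covariance with "repeated avisitn/subject=usubjid type=un".

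**Fallback.** If the unstructured fit does not converge, SAP 5.4.1 says that "either a compound symmetry (first choice) or the first order auto regressive (AR1) (second choice) covariance structure will be used".

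**Definition of change.** The SAP has two.
- SAP 2.1.3.7 and 2.1.3.8 (general): post-baseline means after the start of study treatment, and change exists only where a baseline and a post-baseline value both exist.
- SAP 2.5.2 (NPS): the score at a timepoint less the score at baseline, with no requirement that the timepoint be post-baseline.

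**The concern.** The code asks for one visit more than the model it implements. If 208 and 216 are Weeks 8 and 16, then 201 reads naturally as Treatment Day 1. A change score at the baseline visit is zero for every patient whose Day 1 value is the baseline, so it has no variance.

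An unstructured covariance matrix cannot be estimated properly with a visit of zero variance. The plan would then move to compound symmetry or AR(1). Each imposes a single variance on all visits, so the zero at 201 would pull down the variance used for the Week 16 contrasts. At stake are the primary standard error, confidence interval and p-value, and with them the one-sided 2.5% familywise level in SAP 2.5.2.

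**Working it through.** **Inputs from the documents.** SAP section 3 gives SD 1.8 for the Week 16 change, effect 1.5, one-sided alpha 0.0125 per comparison, 80% power and 10% dropout. SAP 2.5.2 gives a Dunnett test at one-sided 2.5%.

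**Assumptions.** The documents give no Week 8 SD, so s8 = 1.8, 1.5 and 1.2 are shown. Zero change is taken to be stored at 201.

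**1. The plan's sample size.** n = 2(2.241 + 0.842)² × 1.8² / 1.5² = 27.4, so 28 per arm. Then 28 × 1.1 = 30.8, so 31 per arm and 93 in total, as stated. The check below uses 28 evaluable patients per arm, for which the true Week 16 standard error is 1.8 × √(2/28) = 0.481.

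**2. The unstructured fit.** Treatment-by-visit and baseline-by-visit terms fit the 201 rows exactly, so their residual variance is 0. With 93 patients and four mean parameters per visit (three arms and a baseline slope), each hundredfold fall in the 201 variance lowers −2 log REML by 89 × ln 100 = 409.9. For variances of 1, 10⁻², 10⁻⁴, 10⁻⁸ and 10⁻¹⁶ the criterion is 327, −83, −492, −1312 and −2952, up to a constant. It has no minimum.

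**3. Standard error under compound symmetry.** For complete, balanced data the common variance is the average of the visit variances:

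- with 201: ratio to the true SE = √[(0 + s8² + 1.8²) / (3 × 1.8²)]
- without 201: ratio = √[(s8² + 1.8²) / (2 × 1.8²)]

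**4. Familywise error.** This is the probability that the larger of two null statistics, with correlation 0.5, exceeds the Dunnett critical value (about 2.25) multiplied by the ratio. It was obtained by simulation.

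| Assumed Week 8 SD | Ratio with 201 | Familywise error | Ratio without 201 | Familywise error |
|---|---|---|---|---|
| 1.8 | √(6.48/9.72) = 0.82 | 6.3% | 1.00 | 2.5% |
| 1.5 | √(5.49/9.72) = 0.75 | 8.3% | 0.92 | 3.8% |
| 1.2 | √(4.68/9.72) = 0.69 | 10.7% | 0.85 | 5.3% |

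For the first two rows with 201, a nominal 95% interval covers about 89% and 86%. AR(1) with 201 gives ratios of 0.79 to 0.81 at s8 = 1.8, for assumed correlations of 0.9 down to 0.3.

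**5. Check with dropout.** In 1,500 simulated null trials there were 31 patients per arm, both SDs were 1.8, and the correlation (0.7) and missingness (5% at Week 8, 10% at Week 16) were assumed.
- Compound symmetry with 201: mean SE 0.386 against an empirical SD of 0.476; familywise error 7.3%.
- AR(1) with 201: 0.381 against 0.474; also 7.3%.
- Unstructured on 208 and 216 only: 0.476 against 0.472; 2.7% (Monte Carlo error about 0.4 points).

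**6. Direction.** Compound symmetry with 201 understates the SE as long as s8² < 2 × 1.8², that is s8 below 2.55.

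**The case against.** The best defence is that the SAP's general rules already empty the 201 rows. The baseline endoscopy precedes randomization, so under SAP 2.1.3.7 it is not post-baseline, change is missing under SAP 2.1.3.8, and PROC MIXED drops those rows. The model text also names follow-up timepoints only. On this reading the listing does no harm. It is a fair reading, but not the only one: the NPS definition in SAP 2.5.2 yields zero at 201, and the code names that visit for analysis without removing its zeros.

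Second, that 201 is baseline is an inference. As read from the PDF, Protocol Table 8-1 marks endoscopy under Run-in Day 1 and not under Treatment Day 1 (the two fall on the same day), so 201 may hold no NPS record. This uncertainty stands. It does not reconcile code and text, because no other scheduled on-treatment NPS visit exists.

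Third, the harm needs a chain of events: zeros stored, a degenerate fit, and the fallback applied to the same rows without anyone noticing. The printed code also needs an edit before it runs, since the Dunnett option stands after the semicolon that closes the LSMEANS statement. The error could be caught then. PROC MIXED itself was not run here; the failure is deduced from the unbounded likelihood.

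Fourth, a reader might infer that the 201 problem passes to the secondary endpoints. The documents do not support that. SAP 5.4.1 provides for visits appropriate to each endpoint, and Protocol 12.5 lists Weeks 4, 8, 12 and 16 for SNOT-22 and UPSIT. Only the fallback order carries over, and the familywise control covers only the two primary hypotheses.

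**Conclusion.** The mismatch between the code in SAP 5.4.1 and the model in SAP 2.5.2 is real and should be corrected. Its effect is conditional. If change is missing at 201, the primary analysis is unaffected. If zeros are stored and the fallback is used, the Week 16 SE is about 0.82 to 0.69 of its true value and one-sided familywise error is about 6% to 11%, given SD 1.8 at Week 16 and an assumed 1.8 to 1.2 at Week 8.

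A reader might conclude that the trial as planned runs at a 6% to 11% error rate. The documents do not support that: the figure depends on how the dataset is built, on which the SAP's two definitions of change disagree, and on the inferred meaning of 201.

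The fallback is a lesser point. A homogeneous structure misstates the Week 16 SE whenever the variance differs between visits, and this matters mainly for the secondary models with four visits. For NPS with 201 removed, the unstructured matrix has only three parameters, and nothing in the documents suggests that it would fail to converge.

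**What to change.** 1. In SAP 5.4.1, change the clause to `where avisitn in (208,216)` and state that baseline rows carry no change value, so that SAP 2.5.2 and 2.1.3.8 agree. A visit-code key would settle what 201 means.
2. For NCS, SNOT-22 and UPSIT, place heterogeneous-variance structures (for example heterogeneous Toeplitz, then heterogeneous compound symmetry or ARH(1)) ahead of compound symmetry and AR(1).
3. For NPS these structures add nothing: with two visits each has two variances and one correlation, which is the unstructured model. If that fit fails, use other starting values or another optimiser, or a Week 16 ANCOVA.
4. If sandwich standard errors are used anywhere, specify a small-sample correction, because uncorrected ones can be too small at about 28 per arm. They also cannot be combined with the Kenward-Roger degrees of freedom in the code.

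The cost is a few lines of SAP code and text, with no change to sample size or data collection. A Week 16 ANCOVA would not use patients who have only a Week 8 score, so it belongs last. The changes should be made before unblinding, so that the covariance structure is not chosen after the results are seen.
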